## 5. Hypotheses and/or Estimations

Formal hypotheses will not be tested in this trial. The study will provide an estimate of the treatment effect, as measured by the difference in RFS of talimogene laherparepvec neoadjuvant therapy followed by surgery compared to surgery alone in subjects with resectable, stage IIIB to IVM1a melanoma.

## 6. Definitions

The definitions of efficacy endpoints are given in [Section 4](#).

- Investigational Product

Investigational product refers to talimogene laherparepvec in this study.

- Study Drug

Study drug is defined as talimogene laherparepvec in this study.

- Screening Phase

The screening phase is the time period after signing the informed consent and before enrollment when study specific laboratory tests and procedures are performed, and medical history is reviewed to confirm subject eligibility for the study.

- Study Day 1

Study day 1 for a subject is defined as the first day that the study drug is administered to the subject or the surgical resection of melanoma tumor lesion(s), whichever is earlier. Study day 1 is the date of randomization if a subject does not

receive talimogene laherparepvec or the surgical resection of melanoma tumor lesion(s). The day before the study day 1 is referred to as study day -1.

- Baseline

Baseline in general refers to study day 1. The baseline value of a parameter (eg, vital signs, laboratory tests and efficacy endpoints) is considered to be the latest value prior to receiving talimogene laherparepvec or the onset of the surgical resection of melanoma tumor lesion(s), whichever is earlier. If subjects that do not receive study therapy or the surgical resection of melanoma tumor lesion(s), the baseline value will be the last record on or prior to the randomization date.

[figure not shown]
- Treatment Period (also Study Treatment Period, Overall Treatment Period)

Study day 1 through 30 days after the last administration of talimogene laherparepvec or 30 days after the surgical resection of melanoma tumor lesion(s), whichever is later.

- Talimogene Laherparepvec Monotherapy Period (Arm 1 Only)

Talimogene laherparepvec monotherapy period starts at the initiation of the first talimogene laherparepvec dose administration and ends before the surgical resection of the melanoma tumor lesion(s), or 30 days after the last administration of talimogene laherparepvec, whichever is earlier.

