9.2 Reporting of Adverse Events

9.2.1 Reporting Procedures for Adverse Events That do not Meet Serious Criteria

The investigator is responsible for ensuring that all adverse events observed by the investigator or reported by the subject that occur after randomization through the safety follow-up visit (ie, 30 [+15] days after surgery) are reported using the applicable CRF (eg, Adverse Event Summary).

The investigator must assign the following adverse event attributes:

- Adverse event diagnosis or syndrome(s), if known (if not known, signs or symptoms),
- Dates of onset and resolution (if resolved),
- Severity [and/or toxicity per protocol],
- Assessment of relatedness to talimogene laherparepvec or surgery, and
- Action taken.

The adverse event grading scale used will be the CTCAE version 3.0. The grading scale used in this study is described in [Appendix A](#). The investigator must assess whether the adverse event is possibly related to talimogene laherparepvec or surgery. This relationship is indicated by a "yes" or "no" response to the question: Is there a reasonable possibility that the event may have been caused by talimogene laherparepvec or surgery?

The investigator must assess whether the adverse event is possibly related to any study-mandated activity and/or procedure (including any screening procedures). This relationship is indicated by a "yes" or "no" response to the question: "Is there a reasonable possibility that the event may have been caused by a study activity and/or procedure"?

The investigator is responsible for reviewing laboratory test results and determining whether an abnormal value in an individual study subject represents a clinically significant change from the subject's baseline values. In general, abnormal laboratory findings without clinical significance (based on the investigator's judgment) are not to be recorded as adverse events. However, laboratory value changes that require treatment or adjustment in current therapy are considered adverse events. Where applicable,

clinical sequelae (not the laboratory abnormality) are to be recorded as the adverse event.

The investigator is expected to follow reported adverse events until stabilization or reversibility.

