**Figure 1. Example of Treatment Period and T-VEC Monotherapy Period**

- Treatment-Emergent Adverse Events

Treatment-emergent adverse events are events occurring during the Treatment Period. Adverse events occurring on the same day of the start or end day of the treatment period will be counted as treatment-emergent adverse event unless there is evidence to indicate otherwise (eg, the checkbox in CRF, which indicates a AE

onset is prior to first dose of talimogene laherparepvec or surgical resection, is checked).

- Treatment Emergent Death

Treatment emergent death is defined as any death that occurs during the treatment period. Any treatment emergent death will be reported as an SAE.

- Safety Follow-Up

Safety follow-up will be performed approximately 30 (+ 15) days after the last dose of talimogene laherparepvec or the completion of the surgical resection of melanoma tumor lesion(s), whichever is later.

- End of Study

Primary Completion: the time when the last subject is assessed or receives an intervention for the purposes of final collection of data for the primary analysis. The primary completion is anticipated to occur at the later time of either the occurrence of approximately 64 events (local, regional or distant recurrence of melanoma or death) or approximately 2 years after the end of randomization.

End of Trial: the time when the last subject is assessed or receives an intervention for evaluation in the study. The end of trial will occur when the last subject has had the opportunity to complete the long-term follow-up. The end of trial is anticipated to occur approximately 5 years after the end of randomization.

- Long-term Follow-up

Long-term Follow-up will occur every 3 months ( $\pm$  30 days) for 3 years following the safety follow-up visit and then every 6 months ( $\pm$  30 days) until death, subject withdraws full consent, or up to 5 years after the last subject is randomized, whichever is first.

- Concomitant Medications

The concomitant medications include all non-anticancer medication during treatment period.

- On-treatment Procedure/Surgery

The on-treatment surgery includes all surgery subjects receive during treatment period except the protocol specified surgical resection of melanoma lesion(s)

- Prior Systemic Anti-cancer Therapies

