## **10.6 Safety Analyses**

### **10.6.1 Adverse Events**

The Medical Dictionary for Regulatory Activities (MedDRA) version 19.1 or later will be used to code AEs to a system organ class (SOC) and a preferred term within the SOC. The CTCAE version 3.0 will be used to grade severity of AEs.

Only treatment-emergent adverse events (see [Section 6](#) for definition) will be summarized by treatment received. Subject incidence rates of all treatment-emergent, grade  $\geq 3$ , serious, non-serious, treatment related, serious treatment related, non-serious treatment related, events leading to talimogene laherparepvec withdrawal/delay/less than 4ml volume per administration, events leading to cancel the scheduled surgical removal of the melanoma tumor lesion(s), fatal adverse events and local effects on the lesion (i.e., pain, inflammation and ulceration) as well as adverse events of interest will be tabulated by SOC and PT in descending order of frequency within an SOC. For all treatment-emergent adverse events additional summary tables will also be provided by (1) SOC, PT in descending order of frequency within an SOC and worst CTCAE grade, and (2) PT in descending order of frequency.

In addition, certain categories of adverse events occurring within the talimogene laherparepvec monotherapy period and within the period after the start of the first dose of talimogene laherparepvec of  $10^6$  PFU/mL but before the first dose talimogene laherparepvec of  $10^8$  PFU/mL will be summarized separately by system organ class and preferred term in descending order of frequency. These categories of adverse events include all treatment-emergent adverse events, serious treatment-emergent adverse

events, non-serious treatment-emergent adverse events, talimogene laherparepvec related treatment-emergent adverse events.

Subgroups group analyses for age group (< 65, ≥ 65 and < 75, ≥ 75), sex, and race (white vs not white) will be presented for all treatment-emergent adverse events by system organ class and preferred term by treatment received in descending order of frequency.

Narratives of deaths through either the 30 days after the last dose of talimogene laherparepvec or the surgical resection of melanoma tumor lesion(s), whichever is later, will be provided.

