Adverse events after the completion of the surgical resection of melanoma tumor lesion(s) through the 30 days after the last dose of talimogene laherparepvec or the completion of the surgical resection of melanoma tumor lesion(s), whichever is later, will be also be summarized.

A listing of treatment-related AEs reported in long term follow-up will be provided for the final CSR and may be analyzed earlier as part of a program-wide analysis.

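### Treatment-emergent AEs are counted from the first injection in Arm 1 but only from surgery in Arm 2, so Arm 2 pre-surgery AEs reach no planned table and the overall crude incidences cover unequal periods

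*SAP*

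**What the plan says.** SAP section 6 defines Study Day 1 as the "first day that the study drug is administered to the subject or the surgical resection of melanoma tumor lesion(s), whichever is earlier". Randomization serves as Study Day 1 only for subjects who receive neither study drug nor surgery, and SAP section 7.2 leaves those subjects out of the Safety Analysis Set. The Treatment Period runs from "Study day 1 through 30 days after the last administration of talimogene laherparepvec or 30 days after the surgical resection", whichever is later. The definition that follows is: "Treatment-emergent adverse events are events occurring during the Treatment Period".

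SAP section 10.6.1 then restricts the output: "Only treatment-emergent adverse events" are to be summarized, by treatment received and as subject incidence. The categories include grade 3 or higher, serious, related and fatal events, and events that led to cancellation of the planned operation. The same section adds separate summaries for the Arm 1 monotherapy period and a one-sentence summary of events after surgery.

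Collection is wider than tabulation. Protocol section 9.2.1 requires reporting, in both arms, of all adverse events "that occur after randomization through the safety follow-up visit (ie, 30 [+15] days after surgery"). Protocol section 9.2.2 starts SAE collection earlier, at consent.

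**The concern.** Both documents list, as a secondary objective, the safety of neoadjuvant treatment plus surgery compared with surgery alone. The rule for Study Day 1 affects that comparison in two ways.

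First, it discards collected data from one arm. Between randomization and surgery an Arm 2 subject still has unresected tumor, as an Arm 1 subject does early in treatment. Events in that period are tabulated in Arm 1 and not in Arm 2.

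Second, it sets crude percentages over several months beside crude percentages over one month. The trial is descriptive, so readers will interpret the percentages as printed. SAP section 9.4.2 recognizes that differing schedules can bias the detection of recurrence and plans an analysis for it. There is no counterpart for safety.

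The planned table of events that cancelled surgery shows the problem most clearly. An Arm 2 subject whose operation is cancelled outright has received no study treatment, so is outside the Safety Analysis Set. If the operation takes place later, the causing event precedes Study Day 1 and is not treatment-emergent.

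**Working it through.** The documents state no window length, so there is no planned figure to reproduce. The calculation is calendar arithmetic from the schedule.

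**Inputs**
- Arm 1: first dose within 5 days of randomization (protocol 5.1); surgery in weeks 13 to 18 after the 12-week course, or 1 to 6 weeks after the last dose for early stoppers (protocol 3.1).
- Arm 2: surgery after randomization, in weeks 1 to 6 (protocol 7.2.2).
- Week w runs from day 7(w−1)+1 to day 7w; one month is 30.44 days.

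**Length of the treatment-emergent window**
- Arm 1 on schedule: surgery on day 85 to 126, plus 30, gives 115 to 156 days (3.8 to 5.1 months).
- Arm 1, one dose and surgery 7 days later: day 8 + 30 = 38 days.
- Arm 1, week-12 dose (day 78) and no surgery: 78 + 30 = 108 days.
- Arm 2: surgery day + 30 = 31 days (1.0 month).
- Ratio on schedule: 115/31 = 3.7 to 156/31 = 5.0.

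**Collected time that is not tabulated**
- Arm 2: 0 to 41 days before surgery. As a share of randomization to day 30 after surgery, s/(s+31) runs from 0 to 41/72 = 57%.
- Arm 1: at most 5 days.
- In the first 42 days after randomization, Arm 1 is covered for (42−5)/42 = 88% to 100%. If Arm 2 surgery dates are assumed to be spread evenly over days 1 to 42, Arm 2 coverage is the mean of min(43−s, 31)/42, which is 837/1764 = 47%. The cap of 31 is there because the window closes 30 days after surgery.

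**Effect on crude incidence, background events only**

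Assume the same constant hazard in both arms, with 31-day incidence p. Arm 1 incidence over T days is 1−(1−p)^(T/31), with T = 115 and 156.

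| Assumed p (Arm 2) | Arm 1 |
|---|---|
| 5% | 17% to 23% |
| 10% | 32% to 41% |
| 20% | 56% to 68% |

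**Effect when perioperative events are present**
- Each arm has one planned resection. If only perioperative events occur, say 30% in each arm, crude incidence is 30% against 30% and nothing is distorted.
- If that 30% is combined with independent background events at p = 10%, Arm 2 shows 1 − 0.70×0.90 = 37%. Arm 1 shows 1 − 0.70×0.90^(115/31) = 53% to 1 − 0.70×0.90^(156/31) = 59%.

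The values of p and the 30% are assumptions. With equal hazards, on-schedule Arm 1 subjects show the excess at any background rate above zero; its size depends on the rate.

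**The case against.** The strongest defence is that the SAP follows the protocol. Protocol section 7.2.2 has treatment begin at the first dose in Arm 1 and at surgery in Arm 2, and the safety endpoint in both documents is treatment-emergent and treatment-related events. Starting the count at first treatment is conventional. A reader might infer that the SAP contradicts the protocol here. It does not; the problem is what the convention does to this comparison.

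More of the needed output is planned than the overall tables suggest. Protocol section 10.5.4 foresees that post-surgery data, when appropriate, will be shown by treatment actually received. SAP section 10.6.1 includes a post-surgery summary of about 30 days in each arm. It also runs all, serious, non-serious and drug-related events on the monotherapy period, so it would be wrong to infer that every category exists only for the full unequal window. Exposure (SAP 10.6.7) and reasons for not having surgery (SAP 10.2 and 10.6.7) are reported too. These points stand, with limits. The post-surgery sentence names neither arms nor categories, the monotherapy summary concerns Arm 1 only, and none of this recovers Arm 2 pre-surgery events.

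It is also fair that a longer window is partly the regimen itself, so cumulative incidence over each regimen is a legitimate description.

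Exposure-adjusted rates can mislead in the other direction. From randomization, Arm 1 contributes 115 to 161 days and Arm 2 31 to 72 days. With perioperative events alone at 30% in each arm, the rate per subject-month in Arm 1 would be 31/161 = 0.2 to 72/115 = 0.6 times that in Arm 2. Such rates should supplement crude incidence and not replace it.

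**Conclusion.** The concern holds. The two arms start counting at different points, Arm 2 events between randomization and surgery appear in no planned AE table, and an event that cancels Arm 2 surgery outright cannot appear in the table meant for it. The overall by-arm incidence compares about 3.8 to 5.1 months in Arm 1 subjects who follow the 12-week schedule (less in early stoppers) with 1.0 month in Arm 2.

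The size of the distortion is not fixed by the documents. A reader might take 32% to 41% against 10% as the expected inflation of AE incidence generally. That range rests on an assumed 10% background rate and a constant hazard, and it applies to non-surgical events only. Nor do the documents support calling crude incidence non-comparable throughout, since perioperative events are compared fairly.

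The analyses are descriptive and no stopping rule depends on these tables, so this affects how well the comparative safety objective is answered and does not threaten the trial's conduct. It should be corrected, because the data are already collected.

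**What to change.** Amend SAP section 10.6.1 in three places.

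1. Add a by-arm table of all AEs and SAEs from randomization through 30 days after surgery. Include Arm 2 pre-surgery events and randomized subjects whose surgery was cancelled. Those subjects lie outside the Safety Analysis Set, so the table needs its own stated population and an end date for subjects who never reach surgery. Give crude incidence, with exposure-adjusted rates as a supplement.
2. State that the post-surgery summary is shown by treatment received for all, grade 3 or higher, serious, related and fatal events. Name it as the like-for-like comparison between arms, conditional on reaching surgery.
3. Footnote the overall treatment-emergent tables with the unequal window lengths.

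The cost is SAP wording and a few more safety tables. No further data collection and no change to any clinical procedure is needed.

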3. EXPERIMENTAL PLAN

3.1 Study Design

This is a phase 2, multicenter, randomized, open-label study to estimate the efficacy of talimogene laherparepvec as a neoadjuvant treatment followed by surgery compared to surgery alone in subjects with resectable stage IIIB, IIIC, or IVM1a melanoma.

Approximately 150 subjects with completely resectable melanoma and at least one injectable lesion will be randomized 1:1 to receive the following:

- **Arm 1:** Talimogene laherparepvec for 6 doses followed by surgical resection of melanoma tumor lesion(s).
 - **Talimogene Laherparepvec:**

Talimogene laherparepvec will be administered by intralesional injection into the injectable cutaneous, subcutaneous, and nodal tumors initially at a dose of 10^6 plaque forming units (PFU)/mL at day 1 of week 1 followed by a dose of 10^8 PFU/mL at day 1 (± 3 days) of weeks 4, 6, 8, 10 and 12 or until all injectable tumors have disappeared, or intolerance of study treatment, whichever occurs first. Due to the mechanism of action of talimogene laherparepvec, subjects may experience transient growth in existing tumors or the appearance of new tumors prior to maximal clinical benefit of talimogene laherparepvec. Subjects who experience growth in existing tumors or the appearance of new tumors will be allowed to remain on talimogene laherparepvec treatment until week 12 of therapy unless, in the opinion of the investigator, immediate surgical resection or

any other treatment for melanoma is warranted. If talimogene laherparepvec treatment will end prior to week 12, the investigator or designee should notify the sponsor's medical monitor as soon as possible.

– **Surgical Resection of Melanoma Tumor Lesions(s):**

For subjects who complete 12 weeks of talimogene laherparepvec treatment, surgical resection of melanoma lesion(s) will be performed at any time during weeks 13 to 18. Subjects who stop talimogene laherparepvec prior to week 12 due to disappearance of all injectable tumor lesions, intolerance to talimogene laherparepvec, or any other reason will undergo adequate surgical resection of melanoma lesion(s) or tissue where melanoma was present before achieving CR, within 1 to 6 weeks after the last dose of talimogene laherparepvec. If surgery will be performed prior to week 12, the investigator or designee should notify the sponsor's medical monitor as soon as possible. Refer to [Appendix F](#) for surgery guidelines.

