10.5.4 Safety Endpoints

Subject incidence rates of treatment-emergent adverse events (including all adverse events, grade ≥ 3 adverse events, fatal adverse events, serious adverse events, adverse events of interest and events requiring the discontinuation of study drug, local effects on the tumor [ie, pain, inflammation and ulceration]) will be summarized. The Medical Dictionary for Regulatory Activities (MedDRA) will be used to code adverse events to a system organ class (SOC) and a preferred term within the SOC. The CTCAE version 3.0 will be used to grade severity of adverse events. In addition, clinically significant laboratory changes and clinically significant changes in vital signs will be summarized with descriptive statistics. Summary statistics will also be provided for concomitant medications, adjuvant therapy, dose delay, study drug discontinuation, overall exposure, and changes in ECOG performance status. Tables and/or narratives of deaths through 30 days after the latter of the last dose of talimogene laherparepvec or surgery will be provided. The incidence of subjects with herpetic lesions found to be positive for talimogene laherparepvec DNA per qPCR in swab samples collected from lesions suspected to be herpetic in origin and the rate of positive lesions (if any) will be calculated. Potential or known unintended exposure to talimogene laherparepvec, related suspected signs or symptoms, and detection of talimogene laherparepvec in a subject's household member, caregiver, or healthcare provider will be reported.

When appropriate, the safety data during the talimogene laherparepvec monotherapy period before surgical resection will be summarized separately from the safety data after surgical section, which will be summarized by treatment actually received.

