## **3. Study Overview**

### **3.1 Study Design**

This is a phase 2, multicenter, randomized, open-label study to estimate the efficacy of talimogene laherparepvec as a neoadjuvant treatment followed by surgery compared to surgery alone in subjects with resectable stage IIIB, IIIC, or IVM1a melanoma.

Approximately 150 subjects with completely resectable melanoma and at least one injectable lesion will be randomized 1:1 to receive the following:

- Arm 1: Talimogene laherparepvec for 6 doses followed by surgical resection of melanoma tumor lesion(s).
  - Talimogene Laherparepvec:

Talimogene laherparepvec will be administered by intralesional injection into the injectable cutaneous, subcutaneous, and nodal tumors initially at a dose of  $10^6$  plaque forming units (PFU)/mL at day 1 of week 1 followed by a dose of  $10^8$  PFU/mL at day 1 ( $\pm$  3 days) of weeks 4, 6, 8, 10 and 12 or until all injectable tumors have disappeared, or intolerance of study treatment, whichever occurs first. Due to the mechanism of action of talimogene laherparepvec, subjects may experience transient growth in existing tumors or the appearance of new tumors prior to maximal clinical benefit of talimogene laherparepvec. Subjects who experience growth in existing tumors

or the appearance of new tumors will be allowed to remain on talimogene laherparepvec treatment until week 12 of therapy unless, in the opinion of the investigator, immediate surgical resection or any other treatment for melanoma is warranted. If talimogene laherparepvec treatment will end prior to week 12, the investigator or designee should notify the sponsor's medical monitor as soon as possible.

- Surgical Resection of Melanoma Tumor Lesions(s):

For subjects who complete 12 weeks of talimogene laherparepvec treatment, surgical resection of melanoma lesion(s) will be performed at any time during weeks 13 to 18. Subjects who stop talimogene laherparepvec prior to week 12 due to disappearance of all injectable tumor lesions, intolerance to talimogene laherparepvec, or any other reason will undergo adequate surgical resection of melanoma lesion(s) or tissue where melanoma was present before achieving CR, within 1 to 6 weeks after the last dose of talimogene laherparepvec. If surgery will be performed prior to week 12, the investigator or designee should notify the sponsor's medical monitor as soon as possible. Refer to protocol Appendix F for surgery guidelines.

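### The Arm 1 monotherapy safety period is capped at 30 days after the last injection, so up to 17 days before a late operation fall in neither the pre-surgery nor the post-surgery AE summary

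*SAP*

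**What the plan says.** Protocol 10.5.4 states that, when appropriate, "the safety data during the talimogene laherparepvec monotherapy period before surgical resection will be summarized separately from the safety data after surgical section" (the last word evidently means resection). It puts no limit in days on the monotherapy period.

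SAP Section 6 adds one. The Arm 1 monotherapy period starts at the first dose and "ends before the surgical resection of the melanoma tumor lesion(s), or 30 days after the last administration of talimogene laherparepvec, whichever is earlier". SAP 10.6.1 reports certain AE categories for that period: all treatment-emergent, serious, non-serious and talimogene-related. It gives the other half of the split its own summary, which begins "Adverse events after the completion of the surgical resection of melanoma tumor lesion(s) through the 30 days after the last dose" or the completion of surgery, whichever is later.

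The timing of surgery is set elsewhere. For subjects who complete 12 weeks, "surgical resection of melanoma lesion(s) will be performed at any time during weeks 13 to 18" (Protocol 3.1). Those who stop early are operated on "within 1 to 6 weeks after the last dose of talimogene laherparepvec" (SAP 3.1).

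The overall Treatment Period in SAP Section 6 runs without a break from study day 1 to 30 days after the last dose or surgery, whichever is later. AEs in that period are treatment-emergent, and only those are summarised (SAP 10.6.1). The protocol collects AEs for somewhat longer, namely those "that occur after randomization through the safety follow-up visit (ie, 30 [+15] days after surgery" (Protocol 9.2.1).

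**The concern.** The two summaries are meant to describe Arm 1 before and after surgery. Their definitions do not meet. The first can stop at last dose plus 30 days, and the second starts after the operation. When surgery falls later than about a month after the last injection, the days in between belong to neither, and the SAP assigns no other table to them. SAP Section 11, which lists changes from the protocol, does not mention the cap.

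What is at stake is the monotherapy AE profile, including the talimogene-related table. Against a period that runs to surgery, the cap can only lower the number of subjects counted with an event. It does so only for subjects whose operation is late.

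**Working it through.** No figure in the plan addresses this, so the check is calendar arithmetic on the documents' own windows.

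**Inputs**
- Day count: "Study day 1 for a subject is defined as the first day that the study drug is administered" (SAP Section 6, Arm 1). Weeks are taken as counted from that day, so day 1 of week w is 7(w − 1) + 1 and its last day is 7w.
- Last scheduled dose: after week 1, doses fall on day 1 (±3 days) "of weeks 4, 6, 8, 10 and 12 or until all injectable tumors have disappeared" (Protocol 3.1).
- Surgery window: weeks 13 to 18 for completers; 1 to 6 weeks after the last dose for early stoppers.
- Monotherapy cap: last dose + 30 days.

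**Completers**
- Last dose, week 12 day 1: 7 × 11 + 1 = day 78.
- Surgery: 7 × 12 + 1 = day 85 to 7 × 18 = day 126, which is 42 permitted days.
- Interval from last dose to surgery: 85 − 78 = 7 days to 126 − 78 = 48 days.
- Monotherapy coverage ends on day 78 + 30 = 108.
- Uncovered full days before surgery on day s: max(0, s − 1 − 108). For s = 126 this is 17 (days 109 to 125).
- At least one uncovered day arises for s = 110 to 126: 17 of the 42 permitted days.
- With the week-12 dose moved by the ±3-day window (day 75 to 81), the largest interval is 51 to 45 days and the largest gap 20 to 14 days.

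**Early stoppers**
- Largest interval: 6 × 7 = 42 days.
- Largest gap: 42 − 1 − 30 = 11 days.

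**Where a gap AE is counted**
- Overall treatment-emergent tables: yes, because the Treatment Period is continuous to 30 days after surgery.
- Monotherapy summary: no, because the period has ended.
- Post-surgery summary: no, because surgery has not been completed.

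**After the change**
- With the period ending at surgery, the gap falls from up to 17 days (completers) or 11 days (early stoppers) to 0.

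**After surgery, for comparison**
- AEs are collected up to day 45 at the latest and summarised to day 30: 45 − 30 = at most 15 days, and only as far as the subject's actual safety visit.

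**The case against.** Much can be said for the plan as written.

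- The gap touches one descriptive, Arm 1-only split. Every gap AE is still treatment-emergent and appears in the overall, grade ≥ 3, serious and treatment-related tables as applicable. Incidence for a preferred term changes only if the gap event is the subject's first of that term in the period. This stands and limits the size of the point.
- Protocol 10.5.4 says the split is made when appropriate and does not define where monotherapy ends. Last dose plus 30 days is an ordinary exposure window. Neither document says that the split tables must add up to the overall table. This too stands: the protocol is not flatly contradicted. It does describe the period as the one before resection, however, and nothing explains why its last days should go unsummarised.
- SAP Figure 1, which illustrates the periods, is not reproduced in the text reviewed, so the intent it shows could not be checked.

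A reader might infer more than the documents support:

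- **That the gap hides AEs that cancel surgery.** SAP 10.6.1 gives those events their own table. A subject never operated on has no interval between last dose and surgery, and the change proposed here would leave that subject's period as it is. That late surgery reflects toxicity is possible, but the documents do not show it.
- **That 40% of completers are affected.** 17/42 = 40% is a share of permitted calendar days. It becomes a share of subjects only if operations are spread evenly over the window, and no distribution of surgery dates is given.
- **That AEs on days 31 to 45 after surgery are wrongly discarded and the Treatment Period must be lengthened.** Such AEs do appear in no AE summary table. The long-term follow-up listing does not cover them either: it is confined to treatment-related AEs, and that phase follows the safety visit. But the +15 days is the tolerance on a visit date, and a subject seen on day 30 loses nothing. A fixed 30-day window gives equal observation time and matches the 30-day limit on reporting deaths in Protocol 10.5.4 and SAP 10.6.1. Lengthening it would also shift treatment-emergent deaths, concomitant medications and on-treatment surgery, which SAP Section 6 ties to the same period. That is a trade-off, not a correction.

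**Conclusion.** The point holds for the split between the pre-surgery and post-surgery summaries. The SAP's definitions leave up to 17 days before surgery for completers and up to 11 for early stoppers in neither one. The direction is known: pre-surgery AE incidence can be understated, never overstated, and only for subjects operated on more than about 30 days after their last dose. The effect on any reported rate is not known, because the documents give neither surgery dates nor AE rates.

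The 17-day figure assumes that weeks run from the first dose and that the week-12 dose is given on its nominal day. If that dose were missed (last dose day 64) and surgery still fell on day 126, the gap would be 126 − 64 − 1 − 30 = 31 days. The documents do not say which surgery window would then apply, so the conclusion does not rest on that case.

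The overall treatment-emergent tables and the efficacy analyses are unaffected.

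**What to change.** In SAP Section 6, define the end of the Arm 1 monotherapy period in two cases: immediately before surgery when surgery is performed, and 30 days after the last dose when it is not. State which summary takes AEs with onset on the day of surgery, because one period now ends before the operation and the other starts after its completion. The two summaries then cover the Treatment Period of operated subjects without a gap. Check Figure 1 against the new wording.

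Leave the 30-day Treatment Period unchanged. At most, add a supplementary listing, for both arms, of AEs with onset after day 30 up to the safety follow-up visit.

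The cost is a sentence or two of SAP text and one date derivation, on data already collected. The monotherapy period will vary more in length between subjects, so its duration should be shown beside the incidence. The listing is one further output.
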